- If a subject wishes to prematurely discontinue from the study during the Follow-Up Period, he/she will return for a clinic visit and undergo the Month 12 assessments prior to discharge.
- On Day 1 (Baseline), subjects will receive the first dose of study drug; however, Baseline assessments will be performed prior to dosing.

7. Day 1 will occur within 14 days after the final visit of Study HZNP-TEP-301 (Week 24 for proptosis non-responders and up to Week 72 for subjects who relapse).
8. Dosing will be adjusted if there is a change in weight during the Treatment Period. The weight obtained at Week 12 can be used in dose calculations beginning at Week 12 or Week 15.
9. If Day 1 of the extension study occurs on the same day as the final visit of HZNP-TEP-301 (Week 24 [or PW1] for proptosis non-responders and Week 72 [or PW2] for subjects who relapse), assessments do not need to be repeated, and the final assessments from the lead-in study will serve as the Baseline assessments for the extension study.
10. Subjects will receive teprotumumab 10 mg/kg on Day 1 followed by 20 mg/kg q3W for the remaining 7 infusions.
11. Phone (or email) contact by research staff focusing on safety and tolerability aspects will be made the day after infusion for the first and second infusions, and thereafter as deemed appropriate. In addition, subjects who experience an infusion-associated event after any subsequent infusion will also be contacted by phone (or email) by research staff the day after the infusion, and thereafter as deemed appropriate.
12. Perform urine pregnancy tests prior to dose (as applicable) for female subjects of childbearing potential (including those with an onset of menopause <2 years prior to Baseline of HZNP-TEP-302, non-therapy-induced amenorrhea for <12 months prior to Baseline of HZNP-TEP-302, or not surgically sterile [absence of ovaries and/or uterus]).
13. Physical exam will include assessment of presence or absence of pretibial myxedema on Day 1 and Week 24/PW of the Treatment Period and Month 12/PW of the Follow-Up Period. If present, measurements of instep and calf will be taken.

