## 9 INVESTIGATIONAL PLAN

### 9.1 Overall Study Design and Plan

This study will be conducted at up to 16 sites in the United States and Europe.

This is a multi-center, open-label extension study of HZNP-TEP-301 examining the safety and efficacy of teprotumumab in the treatment of TED in adult subjects. Subjects who complete the 24-week double-masked Treatment Period in Study HZNP-TEP-301 and are proptosis non-responders or were proptosis responders at Week 24 but meet the criteria for re-treatment due to relapse (see [Section 9.3.4](#)) during the Follow-Up Period of HZNP-TEP-301 will be eligible for enrollment. The study treatment previously administered in HZNP-TEP-301 (teprotumumab or placebo) will remain masked throughout this extension study.

All subjects who choose to participate will receive 8 infusions of teprotumumab (10 mg/kg for the first infusion followed by 20 mg/kg for the remaining 7 infusions) in an open-label fashion. The Baseline (Day 1) Visit of this extension study will occur within 14 days after the final visit of Study HZNP-TEP-301 (Week 24 for proptosis non-responders and up to Week 72 for subjects who relapse). During the open-label Treatment Period, study drug infusions are scheduled for Day 1 (Baseline), and Weeks 3, 6, 9, 12, 15, 18, and 21 (with a final visit at Week 24 of the 24-Week Treatment Period).

All study drug dosing will be performed at the clinic under the supervision of clinic staff, and at any scheduled infusion, the infusion rate may be reduced or the dose may be interrupted or held based on decreased tolerability (see [Section 9.4.6.3.2](#) for details). On each dosing day, scheduled assessments (except for adverse event [AE] and concomitant medication use monitoring, which will be monitored throughout the clinic visit) will be completed prior to study drug dosing. After each of the first 2 infusions, subjects will be contacted by phone/email the following day and will return to the clinic 1 week after the infusion (Weeks 1 and 4) for safety and tolerability assessments; additional phone/email contacts and clinic visits may also be conducted for any subject experiencing an infusion-associated event.

[figure not shown]

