## 9.3 Selection of Study Population

### 9.3.1 Inclusion Criteria

Eligible subjects must meet **all** of the following criteria:

1. Written informed consent.
2. Completed the 24-week double-masked Treatment Period in Study HZNP-TEP-301.
3. Proptosis non-responder (< 2 mm reduction in proptosis in the study eye) at Week 24 of Study HZNP-TEP-301 OR proptosis responder at Week 24 who relapses (see [Section 9.3.4](#)) during the Follow-Up Period of Study HZNP-TEP-301.
4. Subject must be euthyroid with the baseline disease under control, or have mild hypo- or hyperthyroidism (defined as free thyroxine [FT4] and free triiodothyronine [FT3] levels < 50% above or below the normal limits) at the most recent clinic visit. Every effort should be made to correct the mild hypo- or hyperthyroidism promptly and to maintain the euthyroid state for the full duration of the clinical trial.
5. Alanine aminotransferase (ALT) or aspartate aminotransferase (AST)  $\leq 3$  times the upper limit of normal (ULN) or serum creatinine <1.5 times the ULN (according to age) at the most recent clinic visit.
6. Diabetic subjects must have well-controlled disease (defined as HbA1c < 9.0% at most recent clinic visit).
7. Does not require immediate surgical ophthalmological intervention and is not planning corrective surgery/irradiation during the course of the study.
8. Women of childbearing potential must have a negative urine pregnancy test at Baseline/Day 1. Subjects who are sexually active with a non-vasectomized male partner must agree to use 2 reliable forms of contraception during the trial and continue for 180 days after the last dose of study drug. One of the 2 forms of contraception is

recommended to be hormonal, such as an oral contraceptive. Hormonal contraception must be in use for at least one full cycle prior to Baseline. Highly effective contraceptive methods (with a failure rate less than 1% per year), when used consistently and correctly, includes implants, injectables, combined oral contraceptives, some intrauterine devices (IUDs), sexual abstinence or vasectomized partner.

9. Male subjects must be surgically sterile or, if sexually active with a female partner of childbearing potential, must agree to use a barrier contraceptive method from Baseline through 180 days after the last dose of study drug.
10. Subject is willing and able to comply with the prescribed treatment protocol and evaluations for the duration of the study.

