### 9.3.4 Criteria for Responders Who Relapse

If subjects met the response criteria at Week 24 of HZNP-TEP-301 but subsequently experience a disease relapse during the 48-week Follow-Up Period of the lead-in study, they will have the option to enter this open-label extension study (HZNP-TEP-302) and receive 8 infusions of teprotumumab. The criteria to determine relapse is the following:

- Increase in proptosis of  $\geq 2$  mm in the study eye since Week 24 of HZNP-TEP-301, or
- An increase in CAS of  $\geq 2$  points since Week 24 with an absolute CAS of  $\geq 4$  in the study eye following Week 24 of HZNP-TEP-301.
- In addition to one of the bullet points above, the Investigator should also consider the subject's symptomology to ensure a relapse has occurred (e.g., new onset of double vision).

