##### **9.5.6.1 Day 1/Baseline**

The Baseline (Day 1) Visit must occur within 14 days of the final visit of HZNP-TEP-301. If Day 1 of the extension study occurs on the same day as the final visit of HZNP-TEP-301 and an assessment is scheduled for both visits, assessments do not need to be repeated, and the final assessments from the lead-in study will serve as the Baseline assessments for the extension study.

Potential study subjects will be informed fully regarding the nature of the study and possible AEs, and will receive a copy of the ICF for review. Potential study subjects must read the ICF and sign the document after the Investigator has answered all questions to the study candidate's satisfaction. Further procedures can begin only after the ICF has been signed. The original signed ICF will be retained by the Investigator and a copy will be given to the study subject.

Study candidates will be evaluated for study entry according to the stated inclusion and exclusion criteria ([Section 9.3](#)). The Investigator will evaluate the results of all examinations, including

clinical laboratory tests, from the most recent clinic visit and will determine each candidate's suitability for the study. The Investigator must review these results before determining that a candidate is eligible for study drug treatment. The Baseline urine pregnancy test performed for all female candidates of childbearing potential must be negative in order for subjects to be eligible for treatment. The following procedures will be performed at Baseline to establish each candidate's general health and eligibility for enrollment into the study:

- Obtain signed, written informed consent and permission to use Protected Health Information (in accordance with the Health Insurance Portability and Accountability Act [HIPAA]). Refusal to provide this permission excludes an individual from eligibility for study participation. Record date informed consent was given and who conducted the process on the appropriate source documentation.
- Determine study eligibility through review of the inclusion/exclusion criteria (see [Section 9.3](#))
- Obtain predose blood samples for hematology and chemistry (including thyroid, glucose, and HbA1c) analysis (see [Section 9.5.4.6](#) for details concerning test results and study participation).
- Collect predose blood samples for immunogenicity and PK testing.

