6.2.3. Study Baseline and HZN-001 Baseline

The following two definitions of baseline will be utilized for analysis purposes:

- **Study Baseline** will be defined as the last measurement taken prior to first dose in HZNP-TEP-302 (considering unscheduled visits when available). If a Study Baseline value is not obtained in the HZNP-TEP-302 study prior to dosing, the last value measured in HZNP-TEP-301 will be used. Study Baseline comparisons will be provided for all applicable endpoints.
- **HZN-001 Baseline** will be defined as the last measurement taken prior to first dose of HZN-001 whether it occurred in HZNP-TEP-301 or HZNP-TEP-302 (considering unscheduled visits when available). HZN-001 Baseline comparisons will be provided for select assessments of safety, i.e. laboratory assessments, vital signs, ECGs, physical examinations, and ophthalmic examinations.

Change from (Study or HZN-001) Baseline will be defined as the measurement at each time point minus the relevant Baseline value.

The primary objective will be assessed using the Study Baseline.

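### For subjects who start on the day of their last lead-in visit, the proptosis reading that qualified them can also be Study Baseline, so regression to the mean can raise their primary responder rate

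*Protocol*

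**What the plan says.** Two routes lead into the study, and both can turn on proptosis in the study eye. Protocol 9.3.1 item 3 admits a "Proptosis non-responder (< 2 mm reduction in proptosis in the study eye) at Week 24 of Study HZNP-TEP-301". Protocol 9.3.4 admits a lead-in responder whose proptosis has since risen by at least 2 "mm in the study eye since Week 24 of HZNP-TEP-301, or" who meets a CAS criterion instead; the investigator is also asked to weigh symptoms.

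On timing, Protocol 9.1 states: "The Baseline (Day 1) Visit of this extension study will occur within 14 days after the final visit of Study HZNP-TEP-301". Day 1 may therefore be the same day, and then, under 9.5.6.1, "assessments do not need to be repeated, and the final assessments from the lead-in study will serve as the Baseline assessments". Footnote 9 of the Schedule of Assessments (Protocol 2.1) names the shared visit: "Week 24 [or PW1] for proptosis non-responders and Week 72 [or PW2] for subjects who relapse". For non-responders, Week 24 is also the visit that decides eligibility.

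SAP 6.2.3 sets Study Baseline, the reference for the primary endpoint, as the "last measurement taken prior to first dose in HZNP-TEP-302 (considering unscheduled visits when available"). It adds a second way to share a reading: "If a Study Baseline value is not obtained in the HZNP-TEP-302 study prior to dosing, the last value measured in HZNP-TEP-301 will be used". SAP 8.1 counts a subject as a responder after a fall of at least 2 mm from that value at Week 24, provided the fellow eye has not worsened by 2 mm or more. All summaries are descriptive, by lead-in treatment and overall.

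**The concern.** Suppose one noisy reading both admits a subject and serves as the starting point for measuring improvement. Its error then has a positive mean among those admitted, while the error at Week 24 of the extension does not. The observed fall exceeds the true fall by the mean error of the qualifying reading.

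The study has one arm, so no control group carries the same bias. Neither document plans a replicate reading, a confirmatory reading or an analysis by source of baseline. Subjects with a separate Day 1 visit are scheduled for a fresh reading, so the primary table can mix two kinds of baseline. Selection is also stricter among lead-in teprotumumab subjects than among placebo subjects, so the bias can differ between the columns of the planned tables.

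**Working it through.** The plan gives no target rate, power or sample-size basis to reproduce. The check therefore estimates how large the bias could be in subjects whose reading is shared.

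**Inputs.** Protocol 7.1.3.4.2 gives the sponsor's earlier placebo-controlled TED trial: mean (SE) proptosis reduction 2.46 (0.20) mm on teprotumumab and 0.15 (0.19) mm on placebo, with responders 29/42 and 9/43. Assuming the same denominators lie behind the SEs, the SD of change is 0.20 × √42 = 1.30 mm and 0.19 × √43 = 1.25 mm. The error SD of one Hertel reading, σ, is assumed to be 0.5 to 0.75 mm. The placebo SD implies a ceiling of 1.25/√2 = 0.88 mm.

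**Step 1: upward error in the qualifying reading, non-responders.** With changes normally distributed,

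bias = (σ²/SD) × φ(a)/(1 − Φ(a)), where a = (−2 − mean change)/SD.

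- Teprotumumab: a = 0.46/1.296 = 0.355 and φ/(1 − Φ) = 1.037. Bias = 0.25/1.296 × 1.037 = 0.20 mm at σ = 0.5, and 0.5625/1.296 × 1.037 = 0.45 mm at σ = 0.75.
- Placebo: a = −1.85/1.246 = −1.485 and the ratio is 0.142. Bias = 0.03 to 0.06 mm.

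**Step 2: check the model against the reported counts.** The normal model implies that 7% of placebo and 64% of teprotumumab subjects had a reduction of at least 2 mm. The trial's response definition required that reduction together with a CAS reduction, so the true proportions were at least 9/43 = 20.9% and 29/42 = 69.0%. The model therefore understates placebo selection. Setting the admitted fraction to 34/43 and 13/42 gives ratios of 0.364 and 1.139. Bias becomes 0.07 to 0.16 mm on placebo and 0.22 to 0.49 mm on teprotumumab.

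**Step 3: effect on the responder rate, mean true fall 1.5 mm.** With a fresh baseline the rate is Φ(−0.5/S), where S is the SD of the observed change.

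- If every subject falls by exactly 1.5 mm, S = σ√2 and the rate is 24% to 32%.
- If true falls vary so that S = 1.30, as in the earlier trial, the rate is Φ(−0.386) = 35%.

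A shared baseline moves the rate to about Φ((bias − 0.5)/S). For teprotumumab with varying falls this is Φ(−0.231) = 41% to Φ(−0.039) = 48%. Simulation with 2 million subjects per case gives:

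| Group, shared reading | Bias (mm) | Falls vary: shared vs fresh | All fall exactly 1.5 mm: shared vs fresh |
|---|---|---|---|
| Teprotumumab non-responders, normal model | 0.20–0.45 | 41–48% vs 35% (+6 to +13) | 33–48% vs 24–32% (+9 to +16) |
| Same, reported proportions | 0.22–0.49 | 41–50% vs 35% (+6 to +15) | 34–50% vs 24–32% (+10 to +18) |
| Placebo non-responders, normal model | 0.03–0.06 | 36–37% vs 35% (+1 to +2) | 25–34% vs 24–32% (+1 to +2) |
| Same, reported proportions | 0.07–0.16 | 37–39% vs 35% (+2 to +5) | 27–37% vs 24–32% (+3 to +5) |
| Relapsers on proptosis (true regrowth 1.5 or 2 mm, one look) | 0.28–0.59 | 43–53% vs 35% (+8 to +18) | 37–54% vs 24–32% (+13 to +23) |

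A placebo shift of 0.16 mm at σ = 0.75 could add at most about 0.16 × 0.399/1.06 = 6 points, reached when the true fall is near 2 mm. The fellow-eye condition and rounding of readings are not modelled here.

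**Step 4: pooled non-responders.** Assume 1:1 lead-in allocation, equal uptake and every reading shared. Placebo subjects are then about 72% of the group (0.931/(0.931 + 0.361), or 0.791/(0.791 + 0.310)). With varying falls the pooled excess runs from 0.72 × 0.8 + 0.28 × 5.8 = 2 points to 0.72 × 4.5 + 0.28 × 14.8 = 7 points. If only a fraction f of readings is shared, multiply by f; at f = 0.5 it is about 1 to 4 points.

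**The case against.** The strongest reply is that the reuse rule is disclosed, conditional and part of a descriptive study. No test, alpha level or formal comparison between columns is at risk. Same-day entry is one case within a 14-day window, and on any other Day 1 the efficacy assessments are scheduled before dosing. That stands, and it means that none of the figures above is an estimate for the whole study.

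The relapse route is also looser than the simulation. Subjects may qualify on CAS alone and are then not selected on proptosis. The investigator weighs symptoms as well. Nothing says that the visit meeting the relapse criterion must be the final lead-in visit. These points stand and make the relapser row the least certain.

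The SAP does plan responder rates by enrollment type and against HZN-001 Baseline (Table 14.2.1.1.2). These help the reader but do not correct the primary rate. The first separates the groups and leaves the bias inside each. The second equals Study Baseline for lead-in placebo subjects and mixes in the lead-in effect for the others.

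A reader might infer that placebo entrants are essentially unaffected, or that the re-treated column is clearly favoured overall. The documents support neither. At least 21% of placebo subjects in the earlier trial had a reduction of 2 mm or more, so placebo non-responders are selected too. Relapsers may come from either lead-in arm, and the number of shared readings in each column is not given.

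**Conclusion.** The bias is real in mechanism and direction, and limited to subjects whose qualifying reading is also their Study Baseline. Among them, at σ = 0.5 to 0.75 mm and a mean true fall of 1.5 mm:

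- Lead-in teprotumumab non-responders start about 0.2 to 0.5 mm too high. Their responder rate gains about 6 to 13 points when true falls vary, about 15 if entry follows the reported proportions, and about 18 if every subject falls by exactly 1.5 mm.
- Lead-in placebo non-responders start about 0.03 to 0.16 mm too high, worth roughly 1 to 5 points here and at most about 6.
- Relapsers who qualify on proptosis at the shared visit are affected at least as much as teprotumumab non-responders under the model used. Relapsers on CAS alone have no such bias in proptosis.

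These ranges rest on an assumed error SD and on change distributions borrowed from the earlier trial, and they scale with an unknown shared fraction. It would go too far to say that the overall primary rate is inflated by any particular amount. What the plan lacks is a way for the reader to see how many primary responses rest on a qualifying reading.

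**What to change.** 1. In SAP 8.1, define a flag for whether Study Baseline was the qualifying lead-in reading, through same-day entry or the SAP 6.2.3 fallback. Show the primary responder rate and the mean proptosis change split by that flag, by lead-in treatment and by enrollment type, as a sensitivity table. Cells may be small, so exempt this table from the rule in SAP 6.6 that drops subgroups below five, and report counts. The cost is one derived variable, from visit dates and baseline source, and one table. Flagged and unflagged subjects are not randomised groups, so the table shows exposure to the problem and does not measure the bias exactly.

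2. Where enrolment is still open, take proptosis and CAS out of the same-day exemption in footnote 9 of Protocol 2.1, Protocol 9.5.6.1 and SAP 3.4, and let a separate pre-dose Day 1 reading be Study Baseline. CAS belongs here because some relapsers are selected on it and it enters the CAS change and overall response. Both assessments are already on the Day 1 schedule, so the cost is a few minutes per subject.

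The second change has limits. A same-day repeat, normally by the same observer with the same instrument, is not independent: if the two errors correlate at 0.5 (an assumption), it removes about half of the excess. It also does nothing about slower fluctuation of the disease. The reported responder rate may look slightly less favourable.

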#### **9.5.6.2 Week 1**

- Collect blood samples for hematology and glucose testing (see [Section 9.5.4.6](#) for details concerning test results and study participation).
- Collect blood sample for PK analyses. Record date/time of sample collection.
- Perform physical and ophthalmic examinations, including vital signs.
- Enquire about AEs and concomitant medication use.

Subjects will be released from the study center after all of the visit procedures have been completed and instructed to return to the clinic at Week 3.

#### **9.5.6.3 Week 3**

- Obtain predose blood samples for hematology and chemistry (including thyroid, glucose, but not HbA1c) analysis (see [Section 9.5.4.6](#) for details concerning test results and study participation).
- Collect predose urine sample for urinalysis and also for a pregnancy test for females of childbearing potential; the pregnancy test must be negative for the subject to receive study drug.
- Collect predose blood sample for immunogenicity and PK testing.
- Enquire about signs and symptoms and concomitant medications throughout the visit.
- Perform predose 12-lead ECG.
- Obtain study medication vial assignment and volume of study drug to be administered from EDC.

- Monitor vital signs prior to and at the end of the infusion. Additional vital sign monitoring may be performed in the event of infusion-associated AEs (see [Section 9.5.4.3](#) for details).
- Administer study drug and record date, volume and rate of infusion, and start/stop times of dosing.
- Collect blood samples for PK analyses at the end of the infusion.

Subjects will be discharged from the study center after all of the procedures have been completed and will be contacted the following day to enquire about AEs and concomitant medication use. Subjects will be instructed to return to the clinic at Week 4.

#### **9.5.6.4 Week 4**

- Collect blood samples for hematology and glucose testing (see [Section 9.5.4.6](#) for details concerning test results and study participation).
- Collect blood sample for PK analyses. Record date/time of sample collection.
- Collect vital signs.
- Enquire about AEs and concomitant medication use.

Subjects will be released from the study center after all of the visit procedures have been completed and instructed to return to the clinic at Week 6.

#### **9.5.6.5 Week 6**

- Obtain predose blood samples for hematology and chemistry (including thyroid, glucose, but not HbA1c) analysis (see [Section 9.5.4.6](#) for details concerning test results and study participation).
- Collect predose urine sample for urinalysis and also for a pregnancy test for females of childbearing potential; the pregnancy test must be negative for the subject to receive study drug.
- Enquire about signs and symptoms and concomitant medications throughout the visit.
- Perform predose 12-lead ECG.
- Perform predose physical and ophthalmic examinations, including vital signs. Additional vital sign monitoring may be performed in the event of infusion-associated AEs (see [Section 9.5.4.3](#) for details).
- Perform predose efficacy assessments (CAS, Clinical Measures of Severity including proptosis, diplopia and motility restriction).

- Administer predose GO-QoL questionnaire.
- Obtain study medication vial assignment and volume of study drug to be administered from EDC.
- Administer study drug and record date, volume and rate of infusion, and start/stop times of dosing.

Subjects will be discharged from the study center after all of the procedures have been completed and instructed to return for a clinic visit at Week 9.

